## **Summary**

Povidone Iodine (Iodine with water soluble polymer Polyvinylpyrolidone) or PVP-I is a proven and time trusted antiseptic agent having best possible (99.99%) virucidal effect in it's only 0.23% concentration, against all viruses including SARS-Co, MERS-CoV; even in SARS-COV-2 due to it's nonspecific mode of action for virus killing and having no resistance [1,2]. Corona virus is transmitted by/via respiratory droplets or aerosol, produced from sneezing or coughing of infected persons to healthy individual through mouth and nose mainly [5, 6]. The routes of entry of coronavirus in human body are mouth, nose and eye. PVP-I products for gargling the throat and spraying or washing the nose may have a preventive effect on COVID-19 and if it is proved in this study following human trial, this will be a landmark research in COVID-19 pandemic.

In line of this, PVP-I containing oro-nasal spray, proposed Bangasafe, which should be regarded as PONS (Povidone Iodine oro-nasal spray) in this protocol, has been developed and proposed to use against corona virus disease. The proposed clinical trial would assess the safety and efficacy of this virucidal PONS. This oro-nasal spray is prepared following GMP guideline, easily applied and has been found to be safe and effective. The clinical trial proposed here would be conducted in Bangladesh to specifically assess the safety and efficacy concern of this oro-nasal spray among Bangladeshi citizen. For preliminary assessment of efficacy and safety, a small scale randomized controlled trial with about 200 patients who are COVID-19 positive within last 24 hours had already been taken place in Dhaka medical college hospital and the data has been collected from May 2020 to September 2020 which were very much satisfactory [Attachment 2].

## **Introduction**

The corona virus COVID-19 pandemic is the defining global health crisis of our time and the greatest challenge we have faced since World War Two. We have now reached the tragic milestone of two million deaths, and the human family is suffering under an almost intolerable burden of loss. The pandemic is much more than a health crisis; it's also an unprecedented socio-economic crisis. Stressing every one of the countries it touches; it has the potential to create devastating social, economic and political effects that will leave deep and longstanding scars. Every day, people are losing jobs and income, with no way of knowing when normality will return. Small island nations, heavily dependent on tourism, have empty hotels and deserted beaches. The International Labor Organization estimates that 400 million jobs could be lost

## **Background Information**

#### 1. Description of Povidone Iodine

PVP-I is a water-soluble iodophor (or iodine-releasing agent) that consists of a complex between iodine and a solubilizing polymer carrier, polyvinylpyrrolidone. In aqueous solution, a dynamic equilibrium occurs between free iodine  $(I_2)$ , the active virucidal agent, and the PVP-I-complex.

#### 2. Composition

The PONS contains 0.6% PVP-I as an Active Pharmaceutical Ingredients (API) in sterile de-ionized water. The molecular structure of PVP-I is as follow:

Figure: Chemical Structure of Povidone Iodine

#### 3. Product Development, Quality Control and Quality Assurance

Following aspects of raw materials including API, manufacturing in-process steps, finished product are to be real time monitored and produced in Bangladesh Reference Institute for Chemical Measurements (BRiCM), Ministry of Science and Technology which is the nation first and only recognized national reference institute in chemical metrology.

- Raw materials characterization: Appearance, solubility, identification, nitrogen content, iodide value, loss on drying, pH, sulphated ash and available iodine.
- Solvent/diluents characterization: pH, conductivity, total organic carbon, heavy metal (Pb, As), endotoxin, microbial count.
- Product development and quality testing in several stages: pH, available iodine, iodide, UV absorbance, potency.
- Impurity profile testing: 1-Vinyl-2-pyrrolidinone, 2-Pyrrolidinone, heavy metal (Pb)
- Accelerated & real time stability study and shelf-life determination: pH, available iodine, iodide, UV absorbance Up to 3 (three) month at 25°C, 30 °C and 35 °C

#### 4. Mode of Action

The active moiety, non PVP- bound ('free') iodine is released into solution from the PVP- I complex. PVP itself has no microbicidal activity but rather delivers the free iodine to target cell membranes. It is this free iodine that mediates the basic mechanism of action (oxidation of amino acids and nucleic acids in biological structures), which is difficult, if not impossible, to counteract. This basic mechanism of action leads to strong microbicidal activity expressed by multiple modes of action that include the disruption of microbial metabolic pathways, as well as destabilisation of the structural components of cell membranes, causing irreversible damage to the pathogen. Consumed free iodine is then replaced by PVP- bound iodine. The concentration of free iodine is the determining factor of the microbicidal action of PVP- I. In a study investigating the virucidal activity of different disinfectants, electron micrographs revealed how exposure to iodine led to degeneration of surface proteins essential for the spread of enveloped viruses has also been noted. Furthermore, iodine is a scavanger of free radical oxygen species, contributing to anti-inflammatory properties. This interaction ultimately results in microbial death.

Corona virus is transmitted via respiratory droplets or aerosol, produced from sneezing or coughing of infected persons to healthy individual through mouth, nose and eye. After entry into nasopharynx and oropharynx and Eyes virus stayed there for certain period of time. Then it attached with ACE-2 receptor protein in nasopharynx and oropharynx and invade in to deeper cell s in to these areas. PONS containing 0.6 PVP-I will directly kill the virus and also keep the respective person protective layer of PVP-I for considerable time which will give an additional protection for individual user from SARS-CoV-2 virus infection.

#### 5. Dosage and Administration

#### For adult (18 years and above)

Two puffs in mouth & each nostril in 3-4 hours interval not more than 4 times a day.

#### 6. How Supplied

PONS\_aqueous solution containing 0.6%PVP-I is supplied in 30ml amber color High Density Poly Ethylene (HDPE) bottle designed for pharmaceutical packaging to provide adequate protection against sun light.

#### Side effect

#### 7. Contraindications

#### Iodine hypersensitivity

Patients with sensitivity to iodine and polyvinylpyrrolidine should not receive treatment with povidone-iodine. (ref)

Before intervention all participants will be asked about any H/O hypersensitivity of any drug or food or Iodine containing food or drug. If any participant had previous H/O hypersensitivity he/ she will be excluded from the study.

For immediate hypersensitivity (like other food and drugs) could be ascertained by manifestation of hypotension, respiratory distress, skin itching, discomfort, mucosal swelling. If any , necessary treatment will be provided to settle the patient. For delayed hypersensitivity different biochemical test , like FT3, FT4, TSH etc. will also be done.

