## Methodology

#### Study design

It will be a Multicentre, Single blind, Randomized Controlled Trial.

The participant will be divided into three groups namely Group A (384 intervention group and 384 control group), Group B (20 patient) and Group C (10 healthy person).

**Group A** Number of participants 768 COVID-19 positive, moderately ill admitted patient who will receive intervention once (2 puff 0.6% PVP-I in each nostril and 2 puff inside mouth).

Step 1: Enrollment of the study populations by applying inclusion and exclusion criteria

Step 2: Randomization to allocate experimental and controlled group by using table of random number

Step 3: Application of 0.6% PVP-I spray to experimental group and distilled water to control group

Step 4: Follow up (waiting for 2-5 minutes)

Step 5: Collection of nasopharyngeal and oropharyngeal sawab for RT-PCR test for both group

Step 6: Observation of the patients for 30 minutes for possible early adverse effects (if any) and subsequent management (if needed).

Step 7: Analysis data collection, data processing and analysis by using SPSS software.

**Group B** Number of participants 20 asymptomatic to mild COVID -19 patients to whom after single time application of PVP-I oro-nasal spray, RT-PCR test will be done hourly for 4 hours in a single day (to assess the duration of effectiveness of PVP-I oronasal spray).

Step 1: Selection of 20 patients randomly with no or mild symptoms and obtain their consent for the further tests.

Step 2: Collection of 2nd, 3rd and 4th sample from nasopharynx and oropharynx hourly

Step 3: Data collection, data processing and analysis by using SPSS software

**Group C** Number of participants 10 healthy individual who accept intervention 0.6% PVP-I oronasal spray 3-4 hours interval but not more than 4 times a day for 30 days.

Step 1: Selection of 10 healthy volunteers randomly who will be selected for using 0.6% PVP-I Oro-Nasal spray 2 puff inside both nostrils and mouth 3 to 4 times a day for one month.

Step 2: Collection of blood & urine of participants on day 0, 10, 20, 30 for determination of any change in biochemical marker (thyroid, kidney and liver functions will be done)

Step 3: Data collection, data processing and analysis by using SPSS software

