#### **Exclusion Criteria**

- 1. Patients with critical COVID-19 and moderate COVID-19 with other complication.
- 2. Patients having thyroid dysfunction, pregnant or lactating mother.
- 3. It should not be used prior to or after radioiodine scintigraphy or radioiodine treatment of thyroid carcinoma.
- 4. Patients allergic to iodine should be avoided
- 5. Have participated in other clinical study
- 6. Subjects with other severe acute or chronic conditions that may increase the risk of participation in the study and study treatment, or may interfere with interpretation of study results, and judged by the investigator as not suitable for participation in this clinical trial.

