## **Data Collection instrument and Technique**

A preformed semi structured questionnaire and a check list will be used as data collection instrument. Besides medical history sheet and investigation papers of respective participants will also be used. Face to face interview will also be taken.

After receiving written permission from respective hospital authority and obtaining written informed correct data collection will be started. Study personnel at the site will enter data from source documents corresponding to a subject's visit into the protocol-specific paper CRF(Case report form). Subjects will not be identified by name in the study database or on any study documents to be collected by the principle investigator but will be identified by a site number, subject number and initials.

For paper CRFs: If a correction is made on a CRF, the study staff member will line through the incorrect data, write in the correct data and initial and date the change.

The Investigator is responsible for all information collected on subjects enrolled in this study. All data collected during the course of this study must be reviewed and verified for completeness and accuracy by the Investigator. A copy of the CRF will remain at the Investigator's site at the completion of the study (Annexure 3).

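### The protocol names thyroid function tests as the check for delayed hypersensitivity, and no listed step in the patient groups sets a later clinical safety check

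*Protocol*

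**What the plan says.** Protocol section 7, under *Iodine hypersensitivity*, deals with the two kinds of reaction differently. Immediate hypersensitivity is to be recognised by clinical signs (low blood pressure, breathing difficulty, itching, discomfort, swollen mucosa). For the delayed kind the text is: "For delayed hypersensitivity different biochemical test , like FT3, FT4, TSH etc. will also be done". The sentence gives no time and no group.

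Other sections fix where the thyroid tests happen, and each names Group C only: *Study design* (blood and urine on days 0, 10, 20 and 30), the N.B. under *Selection Criteria* (tests before the intervention) and *Clinical Laboratory Measurements*.

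For patients, *Study design* lists:
- Group A: each is a "moderately ill admitted patient who will receive intervention once", with one safety step, "Observation of the patients for 30 minutes for possible early adverse effects".
- Group B: after one application, "RT-PCR test will be done hourly for 4 hours in a single day". The stated purpose is duration of effect, and no safety step is listed.

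Some provisions could pick up later reactions. *Data Collection instrument and Technique* states that "A preformed semi structured questionnaire and a check list will be used as data collection instrument" and that "medical history sheet and investigation papers of respective participants will also be used". *Ethical Issues and Implication* promises free treatment of any adverse reaction. *Risk Management Plan* describes supervision by doctors and nurses, and antihistamine or steroid if hypersensitivity occurs. None of these sets a time.

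**The concern.** The method does not match the harm. Thyroid hormones do not register an allergic reaction, and the protocol itself keeps the two apart: *10. Undesirable effects* ascribes goitre and thyroid over- or under-activity to excess iodine, and mentions anaphylactic reactions separately. The tests also fall in the group with the fewest people, while nearly all sprayed participants are in Groups A and B.

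Freedom from significant side effects is a secondary endpoint, and safe use is one of the two research questions. If later reactions are noted only when a patient complains or a nurse happens to look, recording may differ by patient, by hospital and by arm. Group A patients also have COVID-19, which can itself cause some of the signs, notably respiratory distress. A raw count in the sprayed arm would be hard to read without the same check, at the same time, in the distilled-water arm.

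**Working it through.** **1. The plan's own figure.** Protocol *Sample Size* and SAP section 1 use n = Z²pq/d² with Z = 1.96, p = q = 0.5, d = 0.05: 1.96² × 0.25 / 0.05² = 384.16, stated as 384 and applied to each Group A arm. It reproduces.

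**2. Listed safety steps, side by side.**

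| Group | Sprayed | Early safety step | Later safety step | Thyroid tests |
|---|---|---|---|---|
| A, intervention | 384 | 30 minutes | none listed | none listed |
| A, control | 0 (distilled water) | 30 minutes | none listed | none listed |
| B | 20 | none listed | none listed (swabs to 4 hours) | none listed |
| C | 10 | none listed | days 10, 20, 30 (blood and urine) | days 0, 10, 20, 30 |

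**3. Headcounts.** Group B's first step speaks of further tests, so its 20 patients may already be in the sprayed Group A arm. Sprayed patients are therefore 384 (full overlap) to 384 + 20 = 404 (no overlap). Those with a listed later safety check: 0. Thyroid tests cover 10/(404 + 10) = 2.4% to 10/(384 + 10) = 2.5% of all sprayed participants.

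**4. What 10 volunteers could show, even with a suitable measure.** With no events in n people, the one-sided 95% upper bound on the rate is 1 − 0.05^(1/n): 25.9% for n = 10, against 0.78% for n = 384 and 0.74% for n = 404. This is illustrative; it assumes that everyone is checked.

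**5. Expected delayed reactions.** The documents give no rate. Assumed rates of 0.1%, 0.5% and 1% give:
- in 384 patients: 0.38, 1.92 and 3.84 cases;
- in 404 patients: 0.40, 2.02 and 4.04 cases.

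**6. Precision of a comparison between the Group A arms.** Suppose the signs occur in a proportion p of both arms because of the disease. The 95% half-width of the difference is 1.96 × √(2p(1 − p)/384).

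| Assumed p | Half-width (percentage points) | Events per arm (384p) |
|---|---|---|
| 1% | 1.41 | 3.8 |
| 5% | 3.08 | 19.2 |
| 10% | 4.24 | 38.4 |
| 20% | 5.66 | 76.8 |

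For a true excess of 1 point over a 1% background (2% against 1%), the half-width is 1.96 × √((0.02 × 0.98 + 0.01 × 0.99)/384) = 1.7 points. The interval would be about −0.7 to 2.7 and would include zero.

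**The case against.** The best reply is that this is a slip of terminology. Thyroid change follows prolonged iodine use, Group C is the only group with prolonged use, and biochemical safety is a stated secondary objective. On that reading the tests are in the right place under the wrong name. The sentence is also open-ended: it says the tests are done in addition, and its list is not closed, so clinical signs are not ruled out. This stands in part, and it is why relabelling is half of the fix. It does not supply the missing half, because no sign, other test or time is stated for delayed reactions.

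The second reply is that the risk is low. The protocol says "If any participant had previous H/O hypersensitivity he/ she will be excluded from the study" and, among the exclusion criteria, "Patients allergic to iodine should be avoided"; patients receive a single application under ward supervision. This stands too. With about 0.4 to 4.0 expected cases at the assumed rates, one added check will not settle whether a rare reaction exists.

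The third concerns the choice of signs. Reusing the immediate signs would bring in respiratory distress and hypotension, which the illness may itself cause. That is fair, and skin and mucosal signs should carry the weight.

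A reader might go further and infer that delayed reactions in patients would go wholly unseen, or that a report of none would have no denominator. The documents do not support either. Supervision and treatment have no time limit, medical records are a data source, the checklist and CRF content is not shown, and 384 patients are randomised to each arm. What can be said is that ascertainment may be uneven and that the number actually checked would not be known. Nor does the *Iodine hypersensitivity* section itself confine the tests to 10 volunteers; that follows from the three sections that schedule them.

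**Conclusion.** The point holds as a minor correction to safety ascertainment. The only measure named for delayed hypersensitivity does not measure it, and it is scheduled for 10 people. No listed step sets a safety check after 30 minutes in Group A, or at any time in Group B, so 0 of 384 to 404 sprayed patients have a listed later check. That count covers listed steps only; it does not show that nothing would be recorded.

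That thyroid tests do not detect allergy is general clinical knowledge, consistent with the protocol's own separation of the two harms. The reaction rates and background rates are assumptions. Under them, an identical later check in both arms could limit a moderate excess (half-width 1.4 to 5.7 points) but could neither confirm nor exclude a rare reaction. Neither the primary analysis nor the sample size is affected.

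**What to change.** 1. Describe FT3, FT4 and TSH as thyroid-safety monitoring in Group C, and remove them as the check for delayed hypersensitivity.
2. State that delayed hypersensitivity is ascertained clinically, mainly by rash, itching and mucosal swelling. Record respiratory distress and hypotension as well, but interpret them only against the control arm.
3. Record these on the planned checklist or CRF at one later time, or at discharge if earlier, identically in both Group A arms and in Group B. Use the existing day 10, 20 and 30 contacts in Group C. The documents give no onset time, so the investigators should choose it; about 24 hours is only an example.
4. Report the number checked in each group and the Group A difference with a 95% confidence interval. The chi-square test in SAP section 2 can accompany it, with Fisher's exact test if events are few.

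**Cost.** The change is one corrected sentence and one time point on a planned form, plus sign fields if the form lacks them. At an assumed 1 to 3 minutes per patient, the work is 768 × 1/60 = 12.8 to 788 × 3/60 = 39.4 staff hours, or about 4 to 13 hours per hospital if shared equally among three. No extra visit or blood sample is needed. The downsides are added work on COVID-19 wards and the recording of disease-related events, about 4 to 77 per Group A arm at assumed rates of 1% to 20%.

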#### Thyroid disease

Caution is advised when administering povidone-iodine to patients with thyroid disease. It should not be used prior to or after radioiodine scintigraphy or radioiodine treatment of thyroid carcinoma.

#### Children, infants

Safety and efficacy of the non-prescription use of povidone-iodine products have not been established in infants or children. Use in the pediatric population should be under the prescription of a qualified health care professional; newborn exposure is typically not recommended for umbilical care due to the possibility of inducing hypothyroidism from iodine absorption. Store out of the reach of children.

#### Pregnancy and Breast-feeding mother

Not recommended for pregnant and breast feeding mother. Topical use of povidone-iodine immediately prior to delivery has resulted in iodine overload in breast-feeding infants in the postpartum period, and may lead to transient hypothyroidism.

#### 8. Instructions to the Patient

The package contains a patient information leaflet to facilitate explaining the characteristics of PONS to patients. A copy of the leaflet should be given to each patient. The advantages and disadvantages of PONS should be explained thoroughly to the patient.

#### 9. Interaction with other drugs

Effects of other drug on Povidone Iodine as below:

**Benzalkonium Chloride:** The use of iodine (povidone-iodine) with benzalkonium chloride aqueous solutions may be incompatible.

**Bupivacaine Liposomal/Lidocaine:** Bupivacaine liposomal/Lidocaineshould not come into contact with the product containing povidone-iodine.

Collagenase: Povidone-iodine inactivates collagenase and concurrent use should be avoided.

**Fibrin Sealant, Human:** If povidone-iodine has been used to clean the wound area, thoroughly rinse and dry prior to application of fibrin sealant. The sealer protein and thrombin solutions of Artiss, TachoSil, and Tisseel can be denatured by povidone-iodine.

**Lithium The rapy:** Use with concurrent lithium therapy has been shown to exhibit additive hypothyroidic effects; therefore concurrent administration is not recommended.

#### **10. Undesirable effects**

No significant side effect is reported when recommended dose is administered at defined frequency. Mild irritation and burning sensation for few seconds to minutes may be observed. Anaphylactic reactions, anaphylactoid reactions and anaphylactic shock have been reported uncommonly with products containing Povidone-Iodine or Povidone. Excess Iodine can produce goitre and hypothyroidism or hyperthyroidism. Such effects have occasionally been seen with extensive or prolonged use of Povidone Iodine.

## **Research Question**

- Does 0.6% PVP-I containing oronasal spray kill or reduce spread transmission of SARS-CoV-2 virus residing on nasopharynx and oropharynx of healthy person or healthy carrier before and after exposed to COVID-19 case?
- Does 0.6% PVP-I containing oronasal spray could be safely used amongst healthy individual

or healthy carrier?

## **Objectives of the study**

#### a. Primary Objective

To assess the virucidal efficacy of 0.6% PVP-I against SARS-CoV-2 in nasopharynx and oropharynx in order to use:

- To prevent viral infection before exposure while visiting and treating COVID-19 patients, attending public gatherings, using public transport etc.
- To prevent viral infection after exposure to COVID-19 patients
- To reduce viral load in nasopharynx and oropharynx of COVID-19 patients which is supposed to reduce viral transmission through respiratory route

